7.5.9. Breaking The Blind

If there is a clinical adverse event that the Investigator judges requiring unblinding of study medication, they will promptly contact the Medical Monitor and review the situation. If the consensus is to unblind the subject's treatment, a trained and authorized site user will log into the Emergency Study Code Break Module and will be provided the patient's treatment assignment.

If there is a clinical adverse event that Pharmacovigilance or Regulatory judge requires unblinding of study medication, the Sponsor's internal procedure will be followed.

If any site team member is unblinded for any reason, the Investigator will notify the Sponsor that unblinding has occurred, without revealing the treatment, and document who was unblinded, the reason for doing so, and the date of unblinding in a note to file.

7.5.10. Investigational Medicinal Product Administration Procedure

IA Administration Into The Hip Joint

- IA injections will be performed by the assigned unblinded injector. The injector may choose the numbing agent to be used based on standard of care, if needed
- A 20 gauge or larger, 3.5 inch needle or longer is to be used for injection
- Sterile technique will be used
- Prior to injection, the injection site should be thoroughly cleansed using a bactericidal solution. The injection contents will not be visible to the patient.
- Aspiration must be attempted prior to all injections. If effusion is detected by fluoroscopy, withdraw to near dryness prior to injection
- Either 5 mL of the reconstituted FX006 or 5 mL of normal saline will be injected into the index hip joint. Refer to the Pharmacy Binder for detailed instructions on how to prepare FX006. Reconstitution process should not be visualized by any blinded study staff or by the patients
- Injection into the hip joint will be done with fluoroscopy guidance by the assigned injector (using contrast or air). The injector may choose the position of the hip (e.g., supine position with lower extremity internally rotated) and the approach for injection (e.g., anterior.)
- Patients will be observed per standard of care after the procedure

Refer to the Pharmacy Binder for detailed references on study drug preparation and IA administration.

Post-Injection Care

Patients should be advised to avoid strenuous activities or prolonged weight-bearing activities for approximately 24 to 48 hours following the injection and to also maintain a stable lifestyle with regard to physical activity throughout the duration of the study.

CONFIDENTIAL Page 43 of 72

7.5.11. Treatment Compliance

Study medication will be administered by the unblinded injector in the clinic. Details regarding study medication administration will be documented in the electronic Case Report Form (eCRF). The receipt, dispensation and return/destruction of any study medication will be properly documented.

If for any reason the administration of study medication is stopped before the entire volume is injected, the injector should document the reason for stopping administration.

7.6. Prior and Concomitant Therapy

During the study, all existing (prior to study entry), new or changes in concomitant medications during the course of the study and the associated reasons for use or change will be documented and reported

7.6.1. Allowable Medications/Non-Pharmacologic Therapies

The following medications/non-pharmacological therapies may be taken or used throughout the study:

- Any treatment for a pre-existing condition or for an AE, outside of the study indication, that is not listed as restricted
- Study-allocated rescue medication
- Aspirin for cardio protection at a maximum stable dose of 325 mg per day provided the dose has been stable over the 3 months prior to Screening
- Medical therapy for depression, including selective or non-selective serotonin reuptake inhibitors (SSRIs, NSRIs, SNRIs) and tricyclics *provided* the dose has been stable over the 6 months prior to Screening 1 (See Table 7-1)
- Stable lifestyle with regard to physical activity, physical therapy, acupuncture, TENS, or bracing during the 1 month prior to Screening and expected to remain stable throughout the duration of the study

Table 7-1 below lists the major classes of anti-depressants and examples of commonly prescribed agents by generic and brand name; it is not a complete listing. If a concomitant medication named by a patient being screened is not familiar, please check at https://www.pdr.net or post a query in the General Log.

CONFIDENTIAL Page 44 of 72

Table 7-1: Commonly Prescribed Anti-depressants by Drug Class

Class	Class name	Generic name	Brand names
SSRIs	selective serotonin reuptake	Citalopram	Celexa
	inhibitors	Escitalopram	Lexapro, Cipralex
		Fluoxetine	Prozac, Sarafem
		Fluvoxamine	Luvox
		Paroxetine	Paxil, Seroxat
		Sertraline	Zoloft
SNRIs	serotonin norepinephrine	Tramadol	Ultram
	reuptake inhibitors	Venlafaxine	Effexor
TCAs	tricyclic antidepressants	Amitriptyline	Elavil
		Doxepin	Sinequan
		Imipramine	Tofranil
		Nortriptyline	Aventyl, Noritren, Pamelor
NDRI	norepinephrine-dopamine reuptake inhibitor	Bupropion	Wellbutrin, Zyban

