7.4.3. Exclusion Criteria

Patients fulfilling at least one of the following criteria may not be included in the study:

Disease-related criteria

- 1. Patients who cannot washout of prohibited medications (e.g., opioids or other analgesics) (Refer to Section 7.6.2)
- 2. Diagnosed as secondary OA in the index hip including but not limited to articular fracture, major dysplasia or congenital abnormality, osteochondritis dissecans, acromegaly, ochronosis, hemochromatosis, Wilson's disease, or primary osteochondromatosis, etc.
- 3. Current or any history of ipsilateral chronic knee pain (lasting \geq 3 months)
- 4. Contralateral hip and/or knee pain ≥ 4.0 (0-10 NRS scale) within 1 month prior to Screening visit
- 5. Current or any history of chronic Sciatica (lasting \geq 3 months)
- 6. Current or any historyof acetabular labrum tear in the study hip
- 7. Atrophic osteoarthritis, femoral head necrosis and/or collapse, or subchondral bone insufficiency fracture in the index hip joint determined via central reading
- 8. Current or history of infection in the index hip (e.g., osteomyelitis) or current skin infection at injection site
- 9. Concurrent chronic pain conditions with pain score ≥ 4.0 (0-10 NRS scale) within 1 month prior to Screening 1 visit, including but not limited to:
 - hip impingement syndrome, trochanteric bursalgia
 - peripheral or central neuropathy that may affect sensation of the index hip
 - non-radicular low back pain
 - peripheral nerve entrapment
 - diabetic neuropathy
 - post-herpetic neuralgia
 - post-stroke pain
 - fibromyalgia
- 10. Major surgery or clinically significant trauma (e.g., fracture) of lower limbs within 12 months prior to Screening visit or with ongoing sequelae.
- 11. painDETECT Questionnaire (PD-Q) score > 18 during Screening visit
- 12. History or current evidence of reactive arthritis, rheumatoid arthritis, psoriatic arthritis, ankylosing spondylitis, or arthritis associated with inflammatory bowel disease, systemic lupus erythematosus or other autoimmune diseases
- 13. Any planned surgeries in the lower limbs during the study period

CONFIDENTIAL Page 35 of 72

Previous or concomitant treatment-related criteria

- 14. Presence of surgical hardware or other foreign body in the index hip
- 15. Planned/anticipated surgery that would require use of a restricted medication during the study period
- 16. IA corticosteroid of any joint within 3 months of Screening visit (investigational or marketed, including FX006)

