7.6.2. Prohibited Medications/Non-Pharmacologic Therapies

The following medications should not be taken or used for the duration of the study, after the patient signs informed consent. The washout (at least 5 half-lives after the last dose) must be completed at least 2 days prior to Screening 2 visit.

- Oral non-steroidal anti-inflammatory drugs (NSAIDs)
- Aspirin (>325 mg per day)
- Centrally-acting pain medications (e.g., pregabalin, gabapentin)
- Opioids, Marijuana, Cannabidiol (CBD)
- Topical therapies (e.g., NSAIDs, capsaicin, lidocaine patches, other local treatments) applied to the index hip
- Anesthetic medications injected locally in the index hip (other than lidocaine if used for IA injection procedure)
- Muscle relaxants (e.g., cyclobenzaprine, tetrazepam, diazepam)
- IV, IM, oral, inhaled, intranasal or topical corticosteroids
- IA corticosteroids in any joint
- Any IA intervention in the index hip (e.g., IA viscosupplementation (hyaluronic acid))
- Initiation of or change in medical therapy for depression, including selective or nonselective serotonin reuptake inhibitors (SSRIs, SNRIs, NSRIs) and tricyclics; see Section 7.6.1 for examples of specific agents in each class
- Any investigational drug, device or biologic
- Immunomodulators, immunosuppressives, or chemotherapeutic agents

CONFIDENTIAL Page 45 of 72

- Live (e.g., MMR vaccine, chicken pox vaccine, rotavirus vaccine) or live-attenuated (e.g., FluMist, Zostavax) vaccines
- Changes to lifestyle with regard to physical activity, physical therapy, acupuncture, TENS, or bracing throughout the duration of the study

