- d. After signing the ICF, patients must stop all restricted medications (other than rescue medication). The washout (at least 5 half-lives) must be completed at least 2 days prior to Screening 2 visit.
- e. Rescue medication will be dispensed to the patient at the Screening visit, and a new bottle will be dispensed at each subsequent visit as needed. Drug accountability will be done at each visit
- f. Pregnancy tests will be done in women of child bearing potential. Serum Pregnancy Test to be collected only at Screening visit. Urine Pregnancy Test to be collected prior to injection of study medication and at EOS (when it occurs)
- g. Aspiration must be attempted prior to all injections. If effusion is detected by fluoroscopy guidance, withdraw to near dryness prior to injection
- h. Via Central Laboratory
- i. To be performed under fluoroscopy guidance
- j. To be completed prior to questionnaires
- k. To be completed after APR and PRR training but prior to any other assessments following the sequence in Table 7-5.
- 1. AEs and concomitant medications will be captured from Day 1 (post injection) to EOS visit.
- m. Visit should be conducted within +/- 3 days from scheduled date.
- n. Screening 1 and Screening 2 visits can be combined into one visit provided the patient does not have a washout from prohibited medications. If there is no washout, please perform APR/PRR first, then the questionnaires in order they are shown on Table 7-6, with the WOMAC being completed after APR/PRR, then all subsequent questionnaires as they are listed for Screening 1.

CONFIDENTIAL Page 48 of 72

Table 7-3: Schedule of Study Assessments for Open Label Extension (OLE) Phase

List of Assessments	Second Injection OLE (Week 12 ⁱ , 16, 20, 24) ^{c,n}	Follow-up (every 4 weeks post 2 nd injection) ^{g,n,o}	EOS for OLE e, g, n, p	
Second Injection Criteria	X			
Physical examination			X	
Index Hip Assessment	X	X	X	
Index Hip X-ray ^b			X	
Vital signs	X ^a	X	X	
Weight and BMI			X	
Hematology, Chemistry ^j			X	
Pregnancy Test ^h	X ^{a, o}		X	
Index Hip Aspiration	X ^{a, f, o}			
IMP administration ^{c, k}	X ^{a, o}			
Rescue Medication dispensing and accountability ^d	X	X	X	
Accurate pain reporting and placebo response reduction training ¹	X	X	X	
WOMAC ^m	X	X	X	
PGIC ^m	X	X	X	
SI, HOOS-QOL, EQ-5D-5L ^m	X	X	X	
AE/SAE & ConMeds	To be collected at every visit and whenever applicable			

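### Table 7-1 lists tramadol as an antidepressant that may continue at a stable dose, while Section 7.6.2 and exclusion 1 require opioids to be washed out

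*Protocol*

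**What the plan says.** **Allowed.** Protocol Section 7.6.1 permits throughout the study "Medical therapy for depression, including selective or non-selective serotonin reuptake inhibitors (SSRIs, NSRIs, SNRIs) and tricyclics", on condition that the dose was stable for the 6 months before Screening 1, and points to Table 7-1. The text introducing the table says: "Table 7-1 below lists the major classes of anti-depressants and examples of commonly prescribed agents by generic and brand name". The table's SNRI rows hold two agents, tramadol (Ultram) and venlafaxine (Effexor). The synopsis repeats the allowance and also points to Table 7-1.

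**Prohibited.** Section 7.6.2 lists drugs not to be used after consent, with a washout of at least 5 half-lives completed at least 2 days before Screening 2. Two entries matter here: "Opioids, Marijuana, Cannabidiol (CBD") and "Centrally-acting pain medications (e.g., pregabalin, gabapentin"). For antidepressants the same list bars only starting or changing therapy, and for the agents it refers the reader back: "see Section 7.6.1 for examples of specific agents in each class".

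**Linked rules.** Exclusion 1 in Section 7.4.3 applies to "Patients who cannot washout of prohibited medications (e.g., opioids or other analgesics"). Footnote d of Table 7-2 says: "After signing the ICF, patients must stop all restricted medications (other than rescue medication"). Footnote n says: "Screening 1 and Screening 2 visits can be combined into one visit provided the patient does not have a washout from prohibited medications".

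Tramadol is mentioned nowhere else in the protocol or SAP.

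**The concern.** Tramadol falls on both sides of an operative medication rule. Under Table 7-1 it is an SNRI antidepressant and may continue at a stable dose. As an opioid and centrally acting analgesic, it must be stopped under Section 7.6.2. A coordinator who checks the prohibited list for antidepressants is sent back to the table that names it.

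The rule decides several things:

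- whether the patient needs a washout;
- whether the patient is eligible under exclusion 1;
- whether Screening 1 and Screening 2 may be combined;
- whether continued use is a protocol deviation, which in Part II can affect membership of the Per Protocol population (Protocol Section 9.2.1).

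Two sites could therefore treat the same patient in opposite ways, each citing the protocol. The primary endpoint is change in WOMAC A pain at Week 12, and the protocol otherwise protects it closely: acetaminophen rescue is barred for 48 hours before each visit (Section 7.6.3). Baseline and Week 12 scores taken on a daily opioid run against that design.

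**Working it through.** **1. The two rules side by side**

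| Question | Section 7.6.1 and Table 7-1 | Section 7.6.2 and exclusion 1 |
|---|---|---|
| How tramadol is classed | SNRI antidepressant (named) | Opioid and centrally acting analgesic (by class; not named) |
| Stable dose for 6 months | May continue | No exception for a stable dose |
| Washout before Screening 2 | Not required | Required |
| Screening 1 and 2 combined | Possible | Not possible, because a washout is needed |
| Use at Week 12 | Allowed | Deviation |

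The documents do not classify tramadol. That it is an opioid analgesic is basic pharmacology and the one outside fact used here. Generic and brand names match across the table columns, so the row is not an extraction fault.

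**2. The plan's own power figure**

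Inputs from Protocol Section 9.3.1: difference 0.65, SD 2.0, two-sided alpha 0.05, minimum 212 per arm, planned 220 per arm, 6% discontinuation. The check is a two-sample t-test with standardized difference 0.65 / 2.0 = 0.325.

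- 212 per arm, no dropout: power 91.6%.
- 212 × 0.94 = 199 per arm: power 89.9%.
- 220 × 0.94 = 207 per arm: power 91.0%.

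The stated 90% is reproduced.

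**3. How many patients could be affected**

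The documents give no prevalence of stable tramadol use. I assume 2% to 5%.

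- Part II, every such patient kept on drug: 440 × 0.02 = 8.8 and 440 × 0.05 = 22, so about 9 to 22.
- Part II, half kept on drug: 4.4 to 11.
- Part I, every such patient kept on drug: 70 × 0.02 = 1.4 and 70 × 0.05 = 3.5, so about 1 to 4.

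**4. Worst case for power**

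Assume every such patient stays on tramadol and has no treatment benefit. A fraction p then dilutes the difference to 0.65 × (1 − p).

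| Fraction affected | Diluted difference | Power, 207 per arm | Power, 199 per arm |
|---|---|---|---|
| 0% | 0.65 | 91.0% | 89.9% |
| 2% | 0.637 | 89.8% | 88.7% |
| 5% | 0.6175 | 88.0% | 86.7% |

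The loss is about 1 point at 2% and about 3 points at 5%.

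**5. What is not distorted**

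Patients must still score 5.0 to 9.0 on WOMAC A at Screening 2 and Day 1, so entry pain is held within range whether or not tramadol is taken. Rescue use is counted from acetaminophen tablets only, so tramadol does not enter that count. Which patients take tramadol at entry does not depend on the arm, so no directional bias is expected.

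**The case against.** The strongest case against is that the operative text already settles the likely situation. The Section 7.6.1 allowance covers therapy for depression only, so tramadol taken for pain is outside it. The general allowance in the same section excludes anything listed as restricted. The opioid ban has no stable-dose exception, and Section 7.6.3 and footnote d both require prohibited drugs to be stopped. The table calls itself incomplete and is an aid to identifying drugs, not a list of approvals. On this reading, keeping a patient on tramadol means letting one example row override an unconditional ban.

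Much of this stands. The table leaves a route open; it does not instruct anyone to use it. But the table exists to tell site staff which drugs are antidepressants, and it names tramadol as one. The instruction to look up a drug or post a query covers only unfamiliar medications, so a drug printed in the table prompts no query.

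The objection on size also stands. The prevalence is assumed, and zero benefit in every affected patient is unlikely. With half of such patients kept on drug, power at 207 per arm is 90.4% (2%) or about 89.6% (5%). In Part I every analysis is exploratory.

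On detection, Section 7.6 requires the reason for each medication to be recorded, and SAP Section 4.2.2 codes medications with the WHO dictionary, so tramadol can be found by name. The general-or-restrictive type in the SAP Section 4.11.5 listing is less dependable: a site that followed Table 7-1 may enter tramadol as general. The documents do not say how that field is completed, so this is a possibility only.

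**Conclusion.** The concern holds. Table 7-1 contradicts Section 7.6.2 and exclusion 1 on tramadol, and no other text resolves it. It reads as a drafting error in an example table, since nothing suggests that anyone meant to permit an opioid, but the table supports a rule that governs washout, eligibility and deviations in a trial with a pain endpoint.

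The size is small: an upper bound of 9-22 of 440 Part II patients and 1-4 of about 70 in Part I, with a worst-case power loss of roughly 1 to 3 points. This rests on the assumed 2-5% prevalence, on every site following the table, and on no treatment benefit in those patients. The realistic consequence is inconsistent handling between sites and perhaps slight dilution. It should be corrected because the contradiction is clear and costs almost nothing to remove.

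**What to change.** - Delete tramadol (Ultram) from Table 7-1. The synopsis relies on the same table, so the deletion corrects both places.
- Name tramadol in Section 7.6.2, and in the synopsis copy of that list, as an example of a prohibited opioid that needs washout whatever the indication or dose stability. Deletion alone removes the contradiction. Naming the drug also settles the question for sites that have already used the table, and exclusion 1, the combined-screening rule and deviation handling then follow.
- Send sites a short memo before Part II enrollment. The protocol has the Part I analysis finish before any Part II patient enrolls, so there is time.
- For Part I, identify any patient on tramadol from SAP Listing 16.2.9.6 by coded drug name, without relying on the general-or-restrictive type alone.

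The cost is one row deleted, one example added, one site memo and one listing search, with no added procedures or patients.

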7.6.2. Prohibited Medications/Non-Pharmacologic Therapies

The following medications should not be taken or used for the duration of the study, after the patient signs informed consent. The washout (at least 5 half-lives after the last dose) must be completed at least 2 days prior to Screening 2 visit.

- Oral non-steroidal anti-inflammatory drugs (NSAIDs)
- Aspirin (>325 mg per day)
- Centrally-acting pain medications (e.g., pregabalin, gabapentin)
- Opioids, Marijuana, Cannabidiol (CBD)
- Topical therapies (e.g., NSAIDs, capsaicin, lidocaine patches, other local treatments) applied to the index hip
- Anesthetic medications injected locally in the index hip (other than lidocaine if used for IA injection procedure)
- Muscle relaxants (e.g., cyclobenzaprine, tetrazepam, diazepam)
- IV, IM, oral, inhaled, intranasal or topical corticosteroids
- IA corticosteroids in any joint
- Any IA intervention in the index hip (e.g., IA viscosupplementation (hyaluronic acid))
- Initiation of or change in medical therapy for depression, including selective or nonselective serotonin reuptake inhibitors (SSRIs, SNRIs, NSRIs) and tricyclics; see Section 7.6.1 for examples of specific agents in each class
- Any investigational drug, device or biologic
- Immunomodulators, immunosuppressives, or chemotherapeutic agents

CONFIDENTIAL Page 45 of 72

- Live (e.g., MMR vaccine, chicken pox vaccine, rotavirus vaccine) or live-attenuated (e.g., FluMist, Zostavax) vaccines
- Changes to lifestyle with regard to physical activity, physical therapy, acupuncture, TENS, or bracing throughout the duration of the study

7.6.3. Rescue Medication

To standardize pain-relief rescue medication across all patients, starting at screening, patients will discontinue all prohibited medications and follow procedures:

- The designated rescue medication is acetaminophen (paracetamol) 500 mg, one tablet every 4 to 6 hr to a maximum of 6 (six) tablets (3000 mg) per 24 hr period.
- Patients may not take any rescue medication during the 48 hr prior to a study visit.
- Starting at screening and at each study visit, patients will be provided with a sufficient quantity of rescue medication for the interval to the next scheduled visit.
- At each visit, patients will return the bottles provided at the previous visit for rescue medication accountability and be issued a new supply.

7.7. Study Variables

7.7.1. Safety Variables

- Adverse Events
- Physical examinations
- Index hip examinations
- Index hip X-rays
- Vital signs
- Clinical laboratory evaluations (hematology, chemistry)

7.7.2. Efficacy Variables

- WOMAC Osteoarthritis Index (0-10 NRS): pain, stiffness and function domains independently and collectively (Bellamy et al, 1988)
- PGIC: 7-point scale (Farrar et al, 2001; Guy, 1976; Dworkin et al, 2005)
- HOOS-QOL Subscale (http://www.koos.nu/)
- Sleep Interference (SI): Question 9F from the Brief Pain Inventory (Short Form)
- EQ-5D-5L: consists of 2 pages: the EQ-5D descriptive system and the EQ visual analogue scale (EQ VAS) (https://euroqol.org)
- Abbreviated Treatment Satisfaction Questionnaire for Medication (TSQM-9)
- Responder status as defined by:

CONFIDENTIAL Page 46 of 72

- o Proportion of patients experiencing either ≥50%, ≥30% or ≥20% decrease (improvement) in pain) (substantial, at least moderate and minimum clinically important difference, respectively, as defined by (Dworkin et al., 2008)
- Outcome Measures in Rheumatology (OMERACT) Osteoarthritis Research Society International (OARSI) criteria (Pham, 2004)
- Consumption of rescue medication

7.8. Schedule of Study Assessments

A summary of the schedule of assessments is provided in Table 7-2 and Table 7-3. Refer to Section 7.9 for details of each assessment.

CONFIDENTIAL Page 47 of 72

Table 7-2: Schedule of Study Assessments for Double Blind Phase

List of Assessments	Screening 1 ⁿ Day -30 to -1	Screening 2 ⁿ Day -10 to -4	Day 1	Weeks 1, 4, 8 ^m	Week 12 EOS for Double blind phase ^{a, m}
Informed consent	X				
Inclusion/Exclusion Review	X		X ^b		
Medical History/Update	X		X ^b		
Patient Demographics	X				
OA Medical History	X				
Prior Treatments and Medications	X		X^{b}		
Physical examination	X				X
Index Hip Assessment	X		X ^b	X	X
Index Hip X-ray ^c	X				X
Vital signs	X		X ^b	X	X
Height	X				
Weight and BMI	X				X
Hematology, Chemistryh	X				X
ESR	X				
HIV, Hep B/Ch	X				
Pregnancy Test ^f	X ^h		X ^b		X
Washout of restricted pain medication	X ^d				
PD-Q, PHQ-9, GAD-7, PCS, ISI	X				
Randomization			X^{b}		
Second Injection Criteria					X
Index Hip Aspiration			$X^{b, g}$		
IMP administration ⁱ			X		
Rescue Medication dispensing and	Х		X	X	X
accountability ^e	Λ		Λ	A	Λ
Accurate pain reporting and placebo		X	X^{b}	X	X
response reduction training j		N/		77	V.
WOMAC ^k		X	X ^b	X	X
PGIC ^k				X	X
TSQM-9 ^k			L		X
SI, HOOS-QOL, EQ-5D-5L ^k			X ^b	X	X
AE/SAE & ConMeds ¹					X

- a. *The Double-Blind Phase* of the study ends at Week 12. Patients participating in Part I of the study will not receive a second injection but will return to the clinic at Weeks 12, 16, 20, and 24 or up until the time of this amendment. Patients participating in Part II of the study who are eligible for the second injection in the open-label phase at Week 12 will receive an open-label injection of FX006 at Week 12 and return for follow-up visits at Weeks 16, 20, and 24. These patients will complete the study at Week 24. Patients participating in Part II of the study who are not clinically indicated for a second injection at Week 12 will return to the clinic at Weeks 16, 20, and 24 and will receive an open-label injection of FX006 at the first evaluation where the patient has been determined to meet all criteria.
- b. To be collected or assessed prior to injection of study medication
- c. X-ray of weight-bearing anterior-posterior view for index hip will be taken for central reading.
- d. After signing the ICF, patients must stop all restricted medications (other than rescue medication). The washout (at least 5 half-lives) must be completed at least 2 days prior to Screening 2 visit.
- e. Rescue medication will be dispensed to the patient at the Screening visit, and a new bottle will be dispensed at each subsequent visit as needed. Drug accountability will be done at each visit
- f. Pregnancy tests will be done in women of child bearing potential. Serum Pregnancy Test to be collected only at Screening visit. Urine Pregnancy Test to be collected prior to injection of study medication and at EOS (when it occurs)
- g. Aspiration must be attempted prior to all injections. If effusion is detected by fluoroscopy guidance, withdraw to near dryness prior to injection
- h. Via Central Laboratory
- i. To be performed under fluoroscopy guidance
- j. To be completed prior to questionnaires
- k. To be completed after APR and PRR training but prior to any other assessments following the sequence in Table 7-5.
- 1. AEs and concomitant medications will be captured from Day 1 (post injection) to EOS visit.
- m. Visit should be conducted within +/- 3 days from scheduled date.
- n. Screening 1 and Screening 2 visits can be combined into one visit provided the patient does not have a washout from prohibited medications. If there is no washout, please perform APR/PRR first, then the questionnaires in order they are shown on Table 7-6, with the WOMAC being completed after APR/PRR, then all subsequent questionnaires as they are listed for Screening 1.

CONFIDENTIAL Page 48 of 72

Table 7-3: Schedule of Study Assessments for Open Label Extension (OLE) Phase

List of Assessments	Second Injection OLE (Week 12 ⁱ , 16, 20, 24) ^{c,n}	Follow-up (every 4 weeks post 2 nd injection) ^{g,n,o}	EOS for OLE e, g, n, p	
Second Injection Criteria	X			
Physical examination			X	
Index Hip Assessment	X	X	X	
Index Hip X-ray ^b			X	
Vital signs	X ^a	X	X	
Weight and BMI			X	
Hematology, Chemistry ^j			X	
Pregnancy Test ^h	X ^{a, o}		X	
Index Hip Aspiration	X ^{a, f, o}			
IMP administration ^{c, k}	X ^{a, o}			
Rescue Medication dispensing and accountability ^d	X	X	X	
Accurate pain reporting and placebo response reduction training ¹	X	X	X	
WOMAC ^m	X	X	X	
PGIC ^m	X	X	X	
SI, HOOS-QOL, EQ-5D-5L ^m	X	X	X	
AE/SAE & ConMeds	To be collected at every visit and whenever applicable			

- a. To be collected or assessed prior to 2nd injection of study medication only if patient is receiving an open label injection of FX006.
- b. X-ray of weight-bearing anterior-posterior view for index hip will be taken for central reading
- c. Open-label injection of FX006 may occur at either Week 12, 16, 20, or 24 depending on when the patient is clinically indicted to receive a second injection
- d. Rescue medication will be dispensed to the patient at each visit as needed. Drug accountability will be done at each visit
- e. To be performed at Week 24, 28, 32, or 36, depending on timing of second injection
- f. Aspiration must be attempted prior to all injections. If effusion is detected by fluoroscopy guidance, withdraw to near dryness prior to injection
- g. If second injection occurs at Week 12, FU visits occur at Weeks 16, 20, and EOS occurs at Week 24. If second injection occurs at Week 16, FU visits occur at Week 20, 24, and EOS occurs at Week 28, and so on in sequence
- Pregnancy test will be done in women of child bearing potential. Urine Pregnancy Test to be collected prior to injection of study medication and at EOS (when it occurs)
- If patient receives the open-label injection at Week 12, assessments for this visit do not need to be duplicated as per the Week 12 double blind period.
- j. Via Central Laboratory
- k. To be performed under fluoroscopy guidance
- To be completed prior to questionnaires
- m. To be completed after APR and PRR training but prior to any other assessments following the sequence in Table 7-6.
- n. Visit should be conducted within +/- 3 days from scheduled date.
- o. Not performed on Part I patients
- p. Not required for Part I patients discontinued upon implementation of this amendment (Protocol V 3.0; Amendment 2.0)

CONFIDENTIAL Page 49 of 72

